3.12.1.1 Liver Chemistry Follow-up Procedures

The procedures listed below are to be followed if a subject meets the liver chemistry stopping criteria 1 through 5 defined in [Section 3.12.1](#):

- Immediately discontinue study treatment(s).
- Notify the Medical Lead within 24 hr of learning of the abnormality to confirm the subject's study treatment(s) cessation and follow-up.
- Complete the "Safety Follow-Up Procedures" listed below.
- Complete the liver event electronic case report forms (eCRFs). If the event also meets the criteria of a SAE (see [Section 8.2](#)), the SAE data collection tool will be completed separately with the relevant details.
- Upon completion of the safety follow-up permanently withdraw the subject from the study and do not rechallenge with study treatment(s).

Safety Follow-Up Procedures for subjects with ALT ≥ 3 times ULN:

- Monitor subjects **weekly** until liver chemistries (ALT, aspartate aminotransferase [AST], alkaline phosphatase [ALP], and bilirubin) resolve, stabilize or return to within baseline values.

Safety Follow-Up Procedures for subjects meeting stopping criterion 1 (ALT ≥ 3 times ULN and bilirubin ≥ 2 times ULN [or ALT ≥ 3 times ULN and INR > 1.5]):

- **This event is considered an SAE** (see [Section 8.2](#)). Serum bilirubin fractionation should be performed if testing is available. If fractionation is unavailable, urinary bilirubin is to be measured via dipstick (a measurement of direct bilirubin, which would suggest liver injury).
- Make every reasonable attempt to have subjects return to the clinic within 24 hr for repeat liver chemistries, additional testing, and close monitoring (with specialist or hepatology consultation recommended).
- Monitor subjects **twice weekly** until liver chemistries (ALT, AST, ALP, bilirubin) resolve, stabilize or return to within baseline values.
- In addition, every attempt should be made to carry out the liver event follow-up assessments described in [Section 3.12.1.2](#).

3.12.1.2 Liver Chemistry Testing Procedures

For subjects meeting any of the liver chemistry stopping criteria in [Section 3.12.1](#), make every attempt to carry out the liver event follow-up assessments described below. Laboratory tests for

liver events will be performed at the central laboratory. Additional information can be found in the lab manual and SPM.

- Viral hepatitis serology, including:
 - Hepatitis A IgM antibody
 - Hepatitis B surface antigen and Hepatitis B Core Antibody (IgM)
 - Hepatitis C RNA
 - Cytomegalovirus IgM antibody
 - Epstein-Barr viral capsid antigen IgM antibody (or if unavailable, then obtain heterophile antibody or monospot testing)
- Blood sample for pharmacokinetic (PK) analysis, obtained within 20 days of the last dose of study treatment(s). Record the date and time of the PK blood sample draw and the date and time of the last dose of study treatment(s) prior the blood sample draw on the eCRF. If the date or time of the last dose is unclear, provide the subject's best approximation. If the date or time of the last dose cannot be approximated, or if a PK sample cannot be collected within the 20-day period following the last dose, do not obtain a PK sample. Instructions for sample handling and shipping are found in the Study Procedures Manual (SPM).
- Serum creatine phosphokinase (CPK) and lactate dehydrogenase (LDH).
- Fractionate bilirubin, if total bilirubin ≥ 2 X upper limit of normal (ULN).
- Obtain a complete blood count (CBC) with differential to assess eosinophilia.
- Record the appearance or worsening of clinical symptoms indicative of hepatitis or hypersensitivity, such as fatigue, nausea, vomiting, right upper quadrant pain or tenderness, fever, rash or eosinophilia as relevant on the AE eCRF.
- Record the use of concomitant medications, including acetaminophen, herbal remedies or any other over the counter (OTC) medications, or any putative hepatotoxins, on the concomitant medication eCRF.
- Record alcohol use on the liver event alcohol intake eCRF.

Every attempt should be made to obtain the following assessments for subjects with ALT ≥ 3 X ULN and bilirubin ≥ 2 X ULN (>35% direct). These assessments are optional for other abnormal liver chemistries:

- Anti-nuclear antibody, anti-smooth muscle antibody, and Type 1 anti-liver kidney microsomal antibodies.
- Liver imaging (ultrasound, MRI or CT) to evaluate liver disease.
- Liver Imaging and/or Liver Biopsy eCRFs are also to be completed if these tests are performed.
- Serum acetaminophen adduct High Performance Liquid Chromatography (HPLC) assay (quantifies potential acetaminophen contribution to liver injury in subjects with definite or likely acetaminophen use in the preceding week ([James 2009](#))).

3.12.2 QTc Stopping Criteria

QTc-Prolongation ^a	Required adverse event management guidelines	Mandatory dose modification requirements

 • QTc ≥501 msec 	
 • Test serum potassium, calcium, phosphorus and magnesium. If abnormal, correct per routine clinical practice to within normal limits. • Review concomitant medication usage for agents that prolong QTc. • Consider evaluation with cardiologist (recommended). 	
 • Interrupt all study treatments (trametinib and dabrafenib) until QTc prolongation resolves to grade 1 or baseline • If event resolves to grade 1 or baseline, restart study treatment at current dose level • If event does not resolve, permanently discontinue study treatments. • If event recurs, permanently discontinue study treatments.

a. Based on average QTc value of triplicate ECGs. For example, if an ECG demonstrates a prolonged QT interval, obtain two or more ECGs over a brief period, and then use the averaged QTc values of the three ECGs.

Every attempt should be made to obtain a blood sample to test serum potassium, calcium, phosphorus and magnesium levels. If any of these are below the lower limits of normal, correct with supplements to within normal limits.

A review of concomitant medication usage for any medications that may prolong QTc should also be performed.

3.12.3 Left Ventricular Ejection Fraction (LVEF) and Valvular Toxicity Stopping Criteria

3.12.3.1 LVEF Stopping Criteria

Decreases of the left-ventricular-ejection-fraction (LVEF) have been observed in subjects receiving trametinib monotherapy and in combination with dabrafenib. Therefore, ECHOs must be performed to assess cardiac ejection fraction in regular intervals as outlined in the Time and Events Table ([Section 7.1](#)). Dose modification guidance and stopping criteria for LVEF decrease are provided in [Table 3-5](#).

ECHO should be performed at baseline and at follow up visit(s). Electronic copies of all ECHO scans will be collected by Novartis for review. Instructions for submission of ECHO scans are provided in the Study Procedures Manual (SPM).

Table 3-5 Mandatory dose modification and required clinical management for LVEF

LVEF-drop (%) & clinical symptoms	Required adverse event management guidelines	Mandatory dose modification requirements
Asymptomatic: Absolute decrease of >10% in LVEF compared to baseline and ejection fraction below the institution's LLN	
 • Report as SAE. • Closely monitoring LVEF via ECHO, repeat ECHO within 2 weeks. If ECHO does not show LVEF recovery after 2 weeks, repeat ECHO 2 weeks later • If the LVEF recovers within 4 weeks (defined as LVEF ≥LLN and absolute decrease ≤10% compared to baseline) 
 • Repeat ECHO 2, 4, 8 and 12 weeks after re-start; continue in intervals of 12 weeks thereafter. 	Interrupt trametinib (on combination therapy dabrafenib may continue) If the LVEF recovers within 4 weeks, 
 • restart treatment with trametinib dose reduced to levels indicated in Appendix 2, dose reduction column and continue dabrafenib at the same dose level. • If the event recurs at the reduced dose level, permanently discontinue trametinib. On combination therapy dabrafenib may continue

LVEF-drop (%) & clinical symptoms	Required adverse event management guidelines	Mandatory dose modification requirements
	
 ● If repeat LVEF does not recover within 4 weeks. 
 ● Consult with cardiologist (recommended) ● Repeat ECHO after 2, 4, 8, 12, and 16 weeks or until resolution 	
 ● If the event recurs after the subject re-escalated to previous dose level, Interrupt trametinib (on combination therapy dabrafenib may continue) and manage as first event. Note: To restart trametinib, LVEF must return to $\leq 10\%$ decrease compared to original baseline ● If more than two occurrence, permanently discontinue trametinib. On combination therapy dabrafenib may continue 
If LVEF does not recover within 4 weeks
 
 ● Permanently discontinue trametinib, (on combination therapy dabrafenib may continue)
Symptomatic: Resting LVEF $\leq 39\%$ or $>20\%$ absolute reduction from baseline	
 ● Report as SAE. ● Consult with cardiologist (recommended) ● Repeat ECHO after 2, 4, 8, 12, and 16 weeks or until resolution 	
 ● Permanently discontinue trametinib. ● Interrupt dabrafenib ● Restart dabrafenib if LVEF recovers including resolution of symptoms.

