3.6 Criteria for Continuing in the Study

For subjects enrolled on Part A, Part B, Part C, and Part D, the following criteria must be met to advance beyond the first 28 days:

- Subjects have not met discontinuation of treatment criteria ([Section 6.3](#))
- No evidence of progressive disease (See [Section 7.6](#)) defined as no clinical evidence of progression for assessments that do not require imaging/disease assessment or no evidence of radiographic or histologic/morphologic progression if disease assessment included imaging (solid tumor)

Patients will be permitted to continue study treatment beyond initial Investigator-assessed disease progression, as long as they meet the following criteria:

- Investigator assessed clear evidence of clinical benefit
- Tolerance of study drug
- Continuation of study treatment is in the best interest of the patient as determined by the Investigator. For this determination, the investigator should consider all relevant data, such as:

- Absence of symptoms and signs of progressive disease
- No decline in performance status
- Absence of rapid progression of disease or of progressive tumor at critical anatomic sites (e.g., cord compression) that would require urgent medical intervention.
- Patient/guardian is willing to continue on the study

If the Investigator determines that all above criteria are met, the patient may continue study treatment and follow all study related procedures, including tumor assessments, as scheduled in the appropriate Time and Events Tables ([Section 7.1](#) table).

- After each tumor assessment, the investigator must confirm if the patient is still benefitting from study treatment, and document this in patient medical records. Toxicity resolved to baseline or grade ≤ 2 with specific exception of:
 - Specific criteria for Ejection Fraction Results ([Section 3.12.3](#)).
 - For subjects in Part B who are not evaluable for hematological toxicity due to marginal bone marrow function from disease infiltration or prior therapy, the following hematologic criteria must be met:
 - Absolute neutrophil count > 500 cell/ μ L,
 - Platelet count $> 25,000/\mu$ L (without transfusion in ≥ 7 days),
 - No life threatening consequences of anemia (no grade 4 anemia per NCI-CTCAE v4.03) ([NCI 2009](#)).

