3.13 Dose Delay and Modification for Events Considered Related to Trametinib

A maximum of one trametinib dose reduction is allowed. If a second dose level reduction is required, treatment will be permanently discontinued.

Trametinib dose modification guidelines are outlined in [Table 3-6](#) for clinically significant toxicities with exception for following events of special interest:

- rash ([Section 3.13.3](#))
- diarrhea ([Section 3.13.4](#))
- ejection fraction changes ([Section 3.12.3.1](#))
- hypertension ([Section 3.13.5](#))
- prolonged QTc ([Section 3.12.1](#))
- pneumonitis ([Section 3.13.5](#))
- visual changes ([Section 3.13.5](#))
- liver chemistry elevation ([Section 3.12.1](#))

For these refer to the relevant sections for dose modification guidelines for adverse events of special interest as stated above.

If treatment related toxicities occur when dabrafenib is used in combination with trametinib then both treatments should be simultaneously dose reduced, interrupted or discontinued with the exceptions described below.

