3.15 Guidelines for Dose Modifications and Toxicity Management for Combination Therapy

If treatment related toxicities occur when dabrafenib is used in combination with trametinib then both treatments should be simultaneously dose reduced, interrupted or discontinued with the exception shown below:

- Dose modification is necessary for only dabrafenib
 - Mild to moderate pyrexia ([Section 3.15.1](#))
 - Uveitis ([Section 3.13.5](#) and [Section 3.14](#))
- Dose modifications are necessary for only trametinib:
 - Retinal vein occlusions (RVO) and retinal pigment epithelial detachment (RPED) ([Section 3.13.5](#))
 - Left ventricular ejection fraction (LVEF) reduction (asymptomatic, [Section 3.12.3.1](#))
 - Pneumonitis and interstitial lung disease (ILD) (grade 4, [Section 3.13.7](#))

The severity of adverse events (AEs) will be graded utilizing the NCI-CTCAE v4.03 ([NCI 2009](#)). Guidelines for dose modifications and interruptions for management of common toxicities associated with dabrafenib are provided in this section.

Trametinib dose reduction for patients enrolled in all parts of the study should follow dose reduction column in the trametinib dosing nomogram in Appendix 2.

Dabrafenib dose reduction should follow the dose reduction column in the dabrafenib dosing nomogram in Appendix 2 provided for patients enrolled in Part C and Part D, as described below

- Dabrafenib dose modification levels in Part C
 - If a subject is dosed at Dose Level 1, and requires dose reduction, treatment must be discontinued
 - If a subject is dosed at Dose Level 2, and requires dose reduction, follow the dose reduction column in dosing nomogram
- Dabrafenib dose modification levels in Part D.
 - Follow dose reduction column in dosing nomogram

Nomograms for each dosing level are provided in [Appendix 2](#).

If a second dose reduction is required, the treatment should be discontinued.

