6.3 Permanent Discontinuation from Study Treatment

Subjects will receive study treatment until disease progression, death or unacceptable toxicity, including meeting stopping criteria for liver chemistry defined in [Section 3.12.1](#). In addition, study treatment may be permanently discontinued for any of the following reasons:

- serious deviation(s) from the protocol that result in a significant risk to the patient's safety;
- subject becomes pregnant;
- request of the subject or proxy (withdrawal of consent by subject or proxy);
- investigator's discretion;
- a dose delay due to study treatment related toxicity of $>$ 28 days;
- intercurrent illness that prevents further administration of study treatment(s);
- subject is lost to follow-up;
- sponsor terminates the study.

The primary reason study treatment was permanently discontinued must be documented in the subject's medical records and eCRF.

If the subject voluntarily discontinues from treatment due to toxicity, 'AE' will be recorded as the primary reason for permanent discontinuation on the eCRF.

Once a subject has permanently discontinued from study treatment, the subject will not be allowed to be retreated. All subjects who discontinue from study treatment will have safety assessments at the time of discontinuation and during post-study treatment follow-up as specified in Time and Events Table (see [Section 7.1](#)).

Adverse Events must be followed for a minimum of 30 days after the last dose. If it is not practical for the subject to return to the clinic, this data may be collected via telephone from the parent/caregiver/subject (as appropriate).

The discontinuation related safety assessments (same assessments as Final visit in the Time and Events Table) may be completed at any time from the last dose to 30 days after the last dose. Ongoing toxicities should be followed to resolution if at all possible. If the decision to discontinue the patient occurs at a regularly scheduled visit, that visit may become the EOT visit rather than having the patient return for an additional visit.

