Brief Physical examination	Will include height and weight, and assessments of the skin, lungs, cardiovascular system, and abdomen (liver and spleen) [and neurological exam as clinically indicated]	X	X	X	X	X	Every 4 weeks	Every 12 weeks	X
Dermatologic skin assessment	Performed by the investigator (or dermatologist, at the discretion of the investigator). If possible, the same physician should perform each exam for the duration of the study to ensure consistency between evaluations. Photographs of suspect lesions at baseline are recommended with photographs and/or biopsies of any new or changing lesions recommended at subsequent on-study visits.	X	X	X	X	X	Every 4 weeks	Every 12 weeks	X
Plain radiograph of wrist or tibial growth plate	Only in subjects with open growth plates at screening	X				X	Every 24 weeks (6 months)	Every 48 weeks (12 months)	X
Tanner Stage						X	Every 24 weeks (6 months)	Every 24 weeks	X
Urine Pregnancy test	For menstruating females and as required per local applicable regulations	X	X	X	X	X	Every 4 weeks	Every 12 weeks	X
Vital signs	Blood pressure, body temperature, pulse rate, respirations	X	X	X	X	X	Every 4 weeks	Every 12 weeks	X
Ophthalmologic examination	Performed by ophthalmologist. See Section 7.3.2 for details.			X		X	Every 12 weeks	Every 12 weeks	

(All subjects unless specified) week 9- final visit:	STUDY PHASE	TREATMENT WEEK 9+							Final Visit
		Week 9	Week 13	Week 17	Week 21	Week 25	Weeks 25+ (after 6 months)	Weeks 49+ (after 1 year)	
Visit	VISIT WINDOW (\pmdays)	± 3	± 7	± 7	± 7	± 7	± 7	± 7	
ECG	Two copies of the ECG tracing should be obtained at the time of the ECG, one to be kept in the study file for retrospective collection by the sponsor if necessary. ECG data should be reviewed by personnel with experience in this study population	X		X		X	Every 12 weeks	Every 12 weeks	X
Echocardiogram (ECHO)	Copies of all ECHOs will be collected and sent to the study sponsor during the study. An ECHO does not need to be performed at study discontinuation unless one was not performed within the previous 8 weeks.			X		X	Every 12 weeks	Every 12 weeks	X
Concomitant medications	See Protocol Section 9 for list of prohibited and cautionary medications.	X	X	X	X	X	X	X	X
Adverse events	Adverse event assessment should be continuous	X	X	X	X	X	X	X	X
Urinalysis	Routine Urinalysis (See Table 7-6)	X	X	X	X	X	Every 4 weeks	Every 12 weeks	X
Blood Sampling									

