7.3.6 Echocardiogram

The ECHOs will be performed to assess cardiac ejection fraction and cardiac valve morphology for the purpose of study eligibility and during the study as specified in the Time and Events

Table (Section 7.1). Additional ECHO assessments may be performed if clinically warranted. The evaluation of the echocardiographer should include an evaluation for LVEF and both right and left-sided valvular lesions.

Copies of all study ECHOs performed will be required to be provided to the sponsor. The ECHOs will not be reviewed in a real-time basis by the sponsor, but rather held for review at a future time point if a cardiac safety signal is identified.

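### Table 3-5 sets no LVEF-specific mandatory action for a symptomatic fall of more than 10 and up to 20 points to below LLN with LVEF above 39%, although the same fall without symptoms triggers one

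*Protocol*

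**What the plan says.** Table 3-5 (Protocol, Section 3.12.3.1) is the mandatory rule for LVEF decline and sorts patients by size of fall and by symptoms.

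- **Asymptomatic row.** The trigger is "Asymptomatic: Absolute decrease of >10% in LVEF compared to baseline and ejection fraction below the" institution's LLN. Required: report as SAE, repeat ECHO within 2 weeks and interrupt trametinib. Trametinib may restart at a reduced dose if LVEF recovers within 4 weeks and is otherwise stopped for good. Dabrafenib may continue.
- **Symptomatic row.** The trigger is a resting LVEF of 39% or less, or more than 20% "absolute reduction from baseline". Required: report as SAE, follow-up ECHOs, permanent trametinib discontinuation and dabrafenib interruption.

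Other sections point back to this table. Section 3.13 provides Table 3-6 "for clinically significant toxicities with exception for following events of special interest", and ejection fraction changes are on that exception list. The continuation rules in Section 3.6 carve out "Specific criteria for Ejection Fraction Results" and refer to Section 3.12.3. For combination therapy, Section 3.15 says that "both treatments should be simultaneously dose reduced, interrupted or discontinued with the exception shown below". The LVEF entry among its trametinib-only exceptions is limited to asymptomatic reduction.

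Routine on-treatment ECHOs (Section 7.1) fall at Day 28, Week 17 and Week 25, then every 12 weeks. Table 7-4 adds: "An ECHO does not need to be performed at study discontinuation unless one was not performed within the previous 8 weeks".

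**The concern.** The two rows do not meet. Once symptoms appear, a fall of more than 10 and up to 20 points to below LLN, with LVEF still above 39%, leaves the first row and does not enter the second. Followed as written, the mandatory table asks less for a child with symptoms than for one with the same ejection fraction and none.

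Reporting is affected too. The protocol-specific SAE in Section 8.2(g) depends on LVEF meeting the stopping criteria, so it inherits the gap. Section 7.3.6 says the sponsor does not review ECHOs in real time, so central reading would not pick up the case promptly. At stake are a defined treatment interruption, an early repeat ECHO and automatic 24-hour reporting. No endpoint or statistical quantity is involved.

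**Working it through.** **1. The uncovered band.** Let b be baseline LVEF and L current LVEF, in whole percent, reading the table's percentages as points.

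- Asymptomatic row: b − L > 10 and L < LLN.
- Symptomatic row: L ≤ 39 or b − L > 20.
- Covered without symptoms but not with them: 10 < b − L ≤ 20, L < LLN and L > 39. In whole percent, L runs from max(40, b − 20) to min(LLN − 1, b − 11).

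The Protocol gives no numerical LLN, so 50% and 55% are assumed, with baselines from 55% to 75%:

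| Baseline | Band, LLN 50% | Band, LLN 55% |
|---|---|---|
| 55% | 40–44 | 40–44 |
| 60% | 40–49 | 40–49 |
| 65% | 45–49 | 45–54 |
| 70% | none | 50–54 |
| 75% | none | none |

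The band vanishes once b − 20 ≥ LLN, because any fall to below LLN then exceeds 20 points and the symptomatic row applies. The 39% limit catches a fall of 20 points or less only if b − 20 ≤ 39, that is b ≤ 59.

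Example: b = 60%, L = 45%, LLN 50%. The fall is 60 − 45 = 15 points. Without symptoms, 15 > 10 and 45 < 50, so the first row applies. With symptoms, 45 > 39 and 15 ≤ 20, so no row applies.

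**2. Does another section close it?**

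- Table 3-6: ejection fraction changes are excepted from it (Section 3.13). The accompanying symptoms, as separate adverse events, are not. Intolerable Grade 2, Grade 3 or Grade 4 symptoms related to treatment would force interruption; tolerable Grade 2 symptoms would not. The table has no ECHO schedule.
- Section 3.15: on combination, both drugs must be modified together. It does not say whether to reduce, interrupt or discontinue, and sets no ECHO timing.
- Section 8.3.1: symptomatic LVEF decrease is listed without a threshold. A cardiovascular eCRF is due within one week; no dose action is attached.
- Section 8.2: hospitalization or another general criterion makes the event an SAE. Otherwise 24-hour reporting depends on medical judgement under item (f).
- Section 3.2.3.1: a Grade 2 LVEF decrease is a DLT with 24-hour reporting, but only in the first 28 days of the dose-determining parts.

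**3. Time to the next mandatory ECHO.** Under the first row it is at most 2 weeks. On the routine schedule the gaps, ignoring visit windows, are Day 28 (Week 5 column) to Week 17 = 12 weeks, Week 17 to Week 25 = 8 weeks, then 12 weeks. A fall found at a scheduled on-treatment ECHO waits 8 to 12 weeks. A fall found between visits waits less, and before Day 28 about 4 weeks at most.

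**4. Number affected.** Section 1.4 gives ejection fraction decrease in 7% of adults on the combination, with most falls that met interruption criteria being asymptomatic. The Amendment 9 rationale gives 18 patients in Part C and 30 in Part D, so 18 + 30 = 48 and 0.07 × 48 = 3.4 patients with any decrease. Only a minority would be symptomatic, and only some of those would lie in the band.

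**The case against.** The best reply is that a competent investigator would not leave this child on treatment and that the Protocol permits action. Under Section 6.3, "study treatment may be permanently discontinued for any of the following reasons", and investigator's discretion is among them. Section 7.3.6 adds: "Additional ECHO assessments may be performed if clinically warranted". Section 3.14 asks investigators to err on the side of caution. It also sends events without a specific guideline to Table 3-6, which arguably brings that table back when no row of Table 3-5 fits.

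Much of this stands. A reader might infer that nothing but personal judgement protects the child, or that the sponsor would not hear of the event. The documents do not support either: Table 3-6 can force interruption for the symptoms themselves, Section 3.15 compels some joint modification on combination, and the one-week eCRF names symptomatic LVEF decrease.

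The reply still does not fill the gap. Section 3.14 is the dabrafenib section, while Section 3.13 expressly returns ejection fraction changes to Section 3.12.3.1. Even if Table 3-6 applied, it would continue dosing through a tolerable Grade 2 event. Nor can the first row be read as silently covering symptomatic patients, since Section 3.15 repeats the asymptomatic limit. Permission to act is weaker than the mandatory rule that the same fall receives without symptoms.

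**Conclusion.** The gap is real, and it is a safety-rule omission rather than a statistical error. No section sets an LVEF-specific dose action or ECHO interval for the band, and reporting within 24 hours is not automatic outside the DLT window. It deserves correction because the table as written gives the sicker child less mandatory protection.

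The size is modest. About 3 of the 48 combination patients would have any ejection fraction decrease if the adult 7% carried over to children, which is an assumption; fewer would be symptomatic and in the band. A reader might apply 7% to all 139 treated patients (0.07 × 139 = 9.7), but it is a combination rate and the Protocol gives none for monotherapy. A reader might also take 8 to 12 weeks as the delay in every case; it holds only for a fall found at a scheduled on-treatment ECHO, so the supportable statement is up to 12 weeks. The band depends on an LLN the Protocol does not state, and it is empty for high baselines, such as 70–75% with an LLN of 50%.

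**What to change.** State in Table 3-5 that any fall of more than 10 points to below LLN that does not meet the existing symptomatic row requires at least the first-row actions, whether or not symptoms are present: interrupt trametinib, report as SAE, repeat ECHO within 2 weeks. If the patient is symptomatic and on combination, also interrupt dabrafenib, consistent with Section 3.15. Neither drug should restart before symptoms resolve. Have Section 3.15 refer to Table 3-5 for symptomatic LVEF falls.

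Whether trametinib may restart at a reduced dose in this tier or must stop permanently is a clinical choice for the sponsor. Section 3.12.3.2 allows reduced-dose restart after symptomatic valve toxicity once imaging and symptoms recover, but the existing symptomatic LVEF row requires permanent discontinuation. The documents do not settle which should govern here.

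The cost is one table edit and one cross-reference, through a protocol amendment. All cohorts are closed, so on the Amendment 9 figures it reaches 139 − 80 = 59 patients still on treatment, or 59 − 13 = 46 if the 13 rollover patients are not among the 80 who discontinued. No scheduled test is added for other patients.
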